1 PROTOCOL SUMMARY

Title:	Improving Health and Employment Outcomes Through Workplace Opioid Policies
Grant Number:	1R34DA050044-01
Study Description:	We will implement the intervention in three local union health funds, evaluate the implementation using the RE-AIM framework, and collect the data needed to measure effectiveness of the workplace opioid guidelines. We will measure a) the health fund's adoption of policies and programs; b) opioid prescriptions, chronic opioid use, and OUD in health claims and pharmacy data; c) changes in knowledge, attitudes, and beliefs of employers, health fund administrators, and employees; and d) employee participation in employee assistance programs and healthcare recovery services.
Objectives*:	The overall aim is to evaluate the feasibility of implementing workplace opioid guidelines in the construction trades; define and collect measures of implementation and effectiveness. The primary objective is to evaluate a change in opioid misuse and opioid use disorder from medical and pharmacy claims, and worker surveys following a change in policies and programs within health funds. The secondary objective is to evaluate a change in lost time and willingness to seek help among workers who are struggling with opioid misuse or substance use problems on worker surveys.
Endpoints*:	The primary endpoints are a) the change in the proportion of workers with opioid misuse, opioid use disorder and opioid overdose: administrative data and b) in the proportion of workers with opioid misuse: worker surveys from baseline to 6-months. The secondary endpoints are a) the change in the proportion of workers with lost time: worker surveys and b) the proportion of workers who are willing to seek help: worker surveys from baseline to 6-months.
Study Population:	Participants will be members of three participating union health funds. We anticipate these unions will have 33300 members enrolled between 2019-2023, which is the period of data used for the trial. All union members of the participating health funds will be enrolled in the study. We expect the demographics of the participants will reflect the demographics of the membership, which is approximately 8% female, and 90% Caucasian. All participants will be located within the geographical region of the union membership.
Phase* or Stage:	This is a feasibility trial.

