6 STUDY INTERVENTION(S) OR EXPERIMENTAL MANIPULATION(S)

6.1 STUDY INTERVENTION(S) OR EXPERIMENTAL MANIPULATION(S) ADMINISTRATION

6.1.1 STUDY INTERVENTION OR EXPERIMENTAL MANIPULATION DESCRIPTION

The intervention is a set of evidence-based guidelines developed by the research team, with formative work and review by subject matter experts, and stakeholders from the construction industry, many of whom have implemented the policies, programs and benefits suggested in the guidelines. The intervention will provide recommendations across the continuum of disease from prevention (no opioid use), through treatment and recovery. It will also cover the topics for different roles including human resources, upper management, front-line supervisors and healthcare providers involved with the monitoring and treating drug-related issues.

The intervention is intended to be used by the organization, union health fund that provides the health benefits and programs for the union members. The health fund has the fiduciary responsibility to provide health policies, programs, and benefits to maximize the health of the members. The health fund must receive approval for health initiatives from the Labor-Management board of trustees. The target of the intervention is the union members, who are the subjects of the health fund policies, programs, and benefits. The outcomes of the study will be measured by the clinical health claims, and self-reported behaviors of the union members.

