8.3.3 CLASSIFICATION OF AN ADVERSE EVENT

8.3.3.1 SEVERITY OF EVENT

This study will evaluate a group-level intervention of an organization’s opioid-related policies and procedures delivered by union health funds, and disseminated to their membership. We will not collect individual identifiers, thus we will likely not have data on Adverse Events or Serious Adverse Events related to the intervention.

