9 STATISTICAL CONSIDERATIONS

9.1 STATISTICAL HYPOTHESES

This is a feasibility trial to evaluate the ability to recruit and enroll health funds, collect endpoint data for primary and secondary outcome measures, and to collect process measures related to implementation of the intervention with three health funds. There is no formal hypothesis testing in this trial although we will calculate descriptive statistics at baseline and follow-up (6-months) to show change over time. The data will be used to compute statistical power for a future R01 if the current study is successful.

- Primary Endpoint(s):
 - a) We will calculate the Proportion of workers with opioid misuse, opioid use disorder and opioid overdose using administrative data. We will assess change of opioid misuse and opioid use disorder at 6 months following delivery of the intervention
 - b) We will calculate the proportion of workers with opioid misuse from worker surveys. We will assess change in opioid misuse at 6 months following delivery of the intervention.

- Secondary Endpoint(s):
 - a) We will calculate the proportion of workers with lost time using worker surveys. We will assess change in reported lost time at 6 months following delivery of the intervention.
 - b) We will calculate the proportion of workers reporting willingness to seek help for opioid abuse using worker surveys. We will assess change in reported willingness to seek help at 6 months following delivery of the intervention.

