9.2 SAMPLE SIZE DETERMINATION

There were no power sample calculations for this study as it is a feasibility pilot study. The data generated from this study will inform the power calculations for a future R01, if the pilot study is successful.

We estimated the number of participants needed for surveys from the sample sizes needed to document change over time for similar behavior outcomes from past studies. The data will be collected at two points in time (baseline and 6-months after start of the intervention). We will collect cross-sectional data, and calculate the group-level change pre-post intervention. We will collect 300 surveys for each participating health fund at baseline and at 6-months post-intervention, and at 12-months time permitting. This will be a minimum of 1800 surveys, or 2700 surveys time permitting.

We estimated the number of participants for the administrative data from the membership sizes of union health funds from past studies. In past studies, union health fund members have covered 10,200 members. We estimate we will collect administrative data for 10,200 members for each of three health funds (total of 30,600) members.

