9.4 STATISTICAL ANALYSES

9.4.1 GENERAL APPROACH

Outcome data is derived from the administrative claims and worker surveys.

Administrative claims will be collected over two periods (06/01/2019-05/31/22) and (06/01/2022-05/31/2023). All three outcomes of interest are primary outcomes. The analysis will examine the group level change of the outcome, adjusting for length of time in each period, to show a reduction in impaired health or behaviors that may be due to implementation of the intervention.

Worker surveys will be collected by member worker surveys from each health fund at two points in time. The baseline, before implementation of the intervention, and at 6-months after start of implementation. All members will be invited to complete a survey. The desired sample is 300 surveys per health fund at each time point. The outcomes are composed of one or more items in the surveys. Group level statistics will be computed as the proportion of members with a positive response to each outcome. The change in proportion by time point may be due to implementation of the intervention.

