9.4.2 ANALYSIS OF THE PRIMARY ENDPOINT(S)

- a) Administrative Claims
 - a. Outcome variables of interest
 - i. Opioid misuse- “Overlapping Rx” OR “Multiple Rx on same day, different provider”
 - ii. Chronic opioid use- more than 60 days supply in a 90 day window
 - iii. Opioid use disorder- ICD-10 T40* (Poisoning by, adverse effect of and underdosing of narcotics and psychodysleptics) &/Or ICD-10 F11* (opioid related disorders) &/or prescribed MAT (Drug name contained “methadone” or “buprenorphine”; picks up buprenorphine, suboxone, zubsolv, naltrexone, methadone, narcan, and vivitrol)
 - b. Compute statistics for baseline period (06/01/2019-05/31/2022) and follow-up (06/01/2022-05/31-2023)

- i. Categorical data will be presented as N (%), continuous data as median (25th, 75th %tile)
- c. Run comparisons between baseline and follow-up time points
 - i. Comparisons involving two categorical variables will be made using Fisher's exact test
 - ii. Comparisons involving a continuous variable and a categorical variable will be made using Wilcoxon Rank Sum test or Kruskal Wallis test

b) Worker Survey

- a. Outcome variable of interest
 - i. Opioid misuse- Participant responded yes to one of the following two questions:
 - 1. Did you use the pain medication more than prescribed, or for a longer period than prescribed? [pnmed_longer]x
 - 2. Have you used prescription pain medications that were prescribed to someone else? [pnmed_othersrx]x
 - b. Compute the change at 6 months post-intervention (change of opioid misusep) of group-level data collected from groups of health

All endpoints are independent outcomes.

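### Section 9.4.2 tests individual members with Fisher's exact test although the intervention acts on three funds and 9.1 disclaims testing; the p-values ignore fund-level movement and can be too small

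*Combined protocol and SAP*

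**What the plan says.** The intervention is at fund level. Section 8.3.3.1 states: "This study will evaluate a group-level intervention". Section 6.1.1 adds: "The intervention is intended to be used by the organization, union health fund that provides the health benefits". Three funds are planned.

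Section 9.4.1 sets the claims question at the same level: "The analysis will examine the group level change of the outcome, adjusting for length of time in each period". It goes on to say that a reduction may be attributable to implementation.

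The method for comparing baseline with follow-up, in 9.4.2 a) c, is: "Comparisons involving two categorical variables will be made using Fisher's exact test". No fund term, clustering or pairing is named, and no significance level is given.

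Section 9.1 says: "There is no formal hypothesis testing in this trial although we will calculate descriptive statistics". Section 3 adds that the study is not powered for statistical change in the outcomes.

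On size, section 9.2 states: "We estimate we will collect administrative data for 10,200 members for each of three health funds (total of 30,600) members". Section 9.3 describes the full claims population and 9.4.8 analyses it by time point. Section 9.4.7 stratifies the endpoints by fund if more than one fund has adequate data, but names no method.

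**The concern.** Two things do not fit together. First, 9.4.2 prescribes tests that 9.1 says will not be done. Second, the test answers a different question from the one asked. Fisher's null hypothesis is that members are exchangeable between periods, so the only noise it recognises is binomial variation among individuals. The question in 9.4.1 is whether the group-level rate changed because of what the fund did. A change in provider network, pharmacy benefit manager, work volume or local prescribing can move a whole fund's rate from one period to the next with no intervention at all, and the test has no term for that.

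The risk is a small p-value, set beside wording that links change to the intervention, being read as evidence of effect. A member-level test also gives no estimate of how much fund rates vary between years, which the power calculation for a later fund-level trial would need.

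**Working it through.** **Inputs from the documents.** Three funds of 10,200 members: 3 × 10,200 = 30,600, which reproduces the figure in 9.2. The protocol summary has 33,300; this makes little difference (last step).

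**Inputs assumed, because the documents give none.**
- Two-sided 5% level, two equal 12-month windows, no true effect.
- Outcome rate p = 1%, 2% or 5.8%. The last is 0.34 × 0.17 = 0.0578, from the national self-report survey figures in section 2.2. It is not a rate under the claims definition in 9.4.2.
- Period-to-period CV of a fund's rate, s = 0 to 10%.
- Within-member correlation between periods, r = 0, 0.5 or 0.7. Many of the same members appear in both periods, and this makes the test more cautious.

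**Formula.** The variance that the test assumes for the difference in proportions, with N members per period, is V0 = 2p(1−p)/N. The actual variance is V = V0(1−r) + 2(sp)²/3. The false-positive rate is 2[1 − Φ(1.96·√(V0/V))].

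**Worked case, p = 2%, s = 10%, r = 0.**
- V0 = 2 × 0.02 × 0.98/30,600 = 1.281 × 10⁻⁶.
- Fund term = 2 × (0.002)²/3 = 2.667 × 10⁻⁶.
- V = 3.948 × 10⁻⁶ and √(V0/V) = 0.570.
- Rate = 2[1 − Φ(1.117)] = 26%.

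**Results.**

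| Fund CV | r | p = 1% | p = 2% | p = 5.8% |
|---|---|---|---|---|
| 0 | 0 | 5% | 5% | 5% |
| 0 | 0.5 | 0.6% | 0.6% | 0.6% |
| 5% | 0 | 8% | 11% | 22% |
| 5% | 0.5 | 2% | 5% | 17% |
| 10% | 0 | 17% | 26% | 47% |
| 10% | 0.5 | 11% | 22% | 45% |
| 10% | 0.7 | 9% | 20% | 44% |

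Simulation of Fisher's test at r = 0 agrees within about 3 percentage points (at CV 10%: 15%, 25% and 46%).

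**Break-even.** Setting V = V0 gives s = √(1.5·r·V0)/p. At r = 0.5 this is 7.0%, 4.9% and 2.8% for the three rates. Below those values the test is conservative.

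**Within a single fund.** With N = 10,200 and one fund, V0 and the fund term both triple. Their ratio is unchanged, so at r = 0 the false-positive rate is the same: 17%, 26% and 47% at CV 10%.

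**With 33,300 members.** At CV 10% and r = 0: 18%, 28% and 48%.

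**The case against.** The strongest reply is that the study disclaims testing, sets no significance level and is a feasibility trial, so there is no error rate to protect. That stands as far as it goes: success in section 3 does not depend on these p-values. It is also a reason to take them out of 9.4.2.

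A reader might infer that ordinary fund variation will be reported as a significant change, or that it dominates at this sample size. The documents do not support either. They give no fund-level variation, and at CV 5% with correlation 0.5 the rate is at or below about 5% for outcome rates of 1% and 2%. Nor do they show that a p-value will be carried into the next grant application as proof of effect; 9.1 and 9.2 say only that the data will inform power.

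Three further limits stand. The calculation uses equal windows, whereas the plan compares three years with one, so the figures show the mechanism and are not the error rate of the planned comparison. Pooling over funds is inferred from 9.3 and 9.4.8 and is not stated. And 9.4.7 already plans a conditional look by fund. That does not repair the test, because Fisher's test within one fund also ignores that fund's own movement between periods.

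**Conclusion.** The concern holds in a conditional form. The conflict between 9.1 and 9.4.2 needs no assumption and requires an edit. It is also certain that the named test has no allowance for fund-level movement, although the intervention acts on three funds.

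Whether the p-values would in fact be too small depends on quantities the documents do not give. Under the stated assumptions, inflation is likely if fund rates vary between periods by roughly 5-10% or more. With less variation and correlated members, the test can be at or below its nominal level. The largest figures rest on the 5.8% rate, which comes from a self-report survey and may not resemble the claims outcome.

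**What to change.** In 9.4.2, remove Fisher's exact test as the baseline versus follow-up comparison, or state that any p-value is descriptive and is not evidence of effect. Either change brings 9.4.2 into line with 9.1. Make the main result each fund's rate per person-year in each period, its change, and the range over funds, without the adequate-data condition that 9.4.7 attaches.

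Yearly rates by fund, from the dated claims already requested, may be added. They give the between-year fund variance that a future trial's power calculation needs. An interval built on them should be optional and descriptive. For example, 3 funds × 4 years gives 12 log rates; fund effects plus a follow-up indicator leave 12 − 4 = 8 degrees of freedom. In simulation with fund CV 5% and a 5.8% rate, this model rejects in about 5% of trials when nothing is shared across funds. That rises to about 14% with a shared year effect of CV 5%, and to about 39% with a shared decline of 5% a year. The text must therefore say that such an interval does not remove a trend or shock common to all funds, and that it has few degrees of freedom if fewer than three funds enrol (one fund leaves 4 − 2 = 2).

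The cost is a wording change and a small extra table, with wider intervals and fewer small p-values.

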Have you had trouble carrying out normal activities (e.g. job, home, hobbies) because of this trouble in your arms, back, or legs?

- Yes
- No

Have you seen a doctor for this painful condition?

- Yes
- No

Did you miss any days of work because of your pain or discomfort?

- Yes
- No

Have you taken any over-the-counter medications to manage your pain?

- Yes
- No

Have you been prescribed (by a doctor) any pain medication? CHECK ALL THAT APPLY:

- Vicodin
- OxyContin
- Tylenol 3 with codeine
- Percocet
- Darvocet
- Morphine
- Hydrocodone
- Oxycodone
- Other
- I have not been prescribed pain medication.

Did you use the pain medication?

- Yes
- No

Are you currently using this prescription pain medication?

- Yes
- No

Did you use the pain medication more than prescribed, or for a longer period than prescribed?	 Yes  No
Did you use the pain medication for symptoms other than pain, such as to help you sleep, to improve your mood, or to relieve stress?	 Yes  No
Have you used prescription pain medications that were prescribed to someone else?	 Yes  No
In the past 12 months, have you gone to work intoxicated , high, or recovering from the night before?	 Yes  No
In the past 12 months, have you used illicit (illegal) drugs to relieve pain when unable to get pain medications?	 Yes  No

Does your union have any of the following policies related to substance use?

Mandatory drug testing
 Yes
 No
 I don't know

Employee with failed drug tests are given medical treatment/counseling.
 Yes
 No
 I don't know

Does your employer have any of the following policies related to substance use?

	Yes	No	I don't know
Mandatory drug testing			
Safety sensitive jobs (drive equipment, work from heights)			
Light duty work available			
Employee termination for failed drug tests			
Employee given second chance			
		to work if failed drug test	
Naloxone kits are available in			
		the workplace	

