15.1.3 STRATEGIES: HEALTHCARE INSURANCE AND PHARMACY COVERAGE

1. Verify medical providers follow evidence-based practices for prescribing opioids (per the CDC guidelines for chronic noncancer pain and alternative non-opioid treatments when appropriate for acute or chronic pain).
2. Minimize early exposure to opioids by offering non-opioid and non-pharmaceutical pain management options such as physical therapy, chiropractic, acupuncture, cognitive behavioral therapy, and/or mindfulness.
3. Offer behavioral health services to employees (and their dependents) for treatment of mental illness and substance use disorders and follow mental health parity requirements.
4. Insure behavioral counselors and providers are accessible to employees' physical location for in-person sessions, offer a telehealth option, insure treatment hours accommodate the employee's work hours, and offer crisis management hotlines for emergencies.
5. Insure the behavioral health provider has an adequate number of counselors available to minimize wait times for appointments for treatment and work with your provider if they need to expand their network.
6. Consider expanding insurance coverage for screenings, brief intervention, and referral to treatment (SBIRT) for substance use and prescription drug problems through a third party behavioral health or primary care provider in your health system. Visit SAMHSA's [website](#) for more detail on SBIRT.
7. Provide coverage (with reasonable copay) for inpatient and outpatient recovery services and behavioral counseling for those with opioid use disorder.

8. When possible, integrate medical, behavioral, and pharmacy services and health records to improve communication and a collaborative care model.
9. Use **NSC Warn Me Labels** on insurance cards

Pharmacy coverage:

10. Insure employee education on risks of opioid prescriptions, and provide safe disposal for unused medications (either a disposal bag or location).
11. Monitor the supply of prescription opioids as recommended by the CDC minimal number of days (3 to 7), monitor dosage (maximum of 50 morphine milligram equivalent (MME)), and require reauthorization by provider regardless of the reason for the medication [67].
12. Check with your PBM to see if they offer an opioid management program (Example: *Express Scripts*).
13. Coordinate with the physician to consult the Prescription Drug monitoring program (PDMP) before prescribing an opioid to avoid multiple opioid prescriptions [66].

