14. Offer coverage for medication for opioid addiction treatment (i.e. buprenorphine) as this may be a treatment for employees with opioid use disorder.

Prescription Opioids and Pain Management

Opioids are highly effective to control acute pain but high doses and long-term use of prescription opioids quickly leads to addiction and the diagnosable condition called opioid use disorder [68, 69]. Prescription opioids should be judiciously prescribed for short-term acute pain, and carefully monitored by a physician [64]. Health plans, whether sponsored by the employer or union, should seek information from their insurance company and health system to learn about their in-network providers' treatment approach of using prescription opioids for pain management to insure opioids are prescribed appropriately.

Even though opioids are effective for treating acute pain, often non-opioid treatments are equally or more effective for managing pain [70-72]. Alternative treatments may include nonsteroidal anti-inflammatory or non-pharmaceutical treatments like physical therapy, and cognitive behavioral therapy [64, 67]. Employers and unions should consider providing alternative pain treatments as covered services in their benefits plan.

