3. Chronic MSD or recurring acute injuries
4. Other diagnoses

- v. Opioid utilization. Number of workers with:
 1. At least one opioid fill
 2. Ever days supply > 7
 3. Ever MME/day > 50
 4. Ever MME/day > 90
 5. Overlapping Rx
 6. Chronic use (>60 day supply in 90-day period)
 7. Multiple Rx on the same day, same provider
 8. Multiple Rx on the same day, different providers
 9. Misuse
- vi. OUD
 1. N by source (diagnosis, MAT fill, both)

- h. Medical claim/opioid linked data
 - i. Distribution of opioid fills by diagnosis, as captured on linked claim

- b) Worker Surveys
 - a. Worker surveys will be distributed to all members of each health fund at start of project, to collect a sample of 300 surveys. We will collect another sample of 300 surveys after 6 months.
 - b. We will examine the serial cross sectional data (baseline & 6mos) by comparing sample characteristics.
 - Age, x
 - gender, x
 - race, x
 - hisp, x
 - unionbenefits, x
 - employstatus, x
 - time_construction, x
 - months_construction, x
 - constype;x
 - c. We will examine the items related to each of the three outcomes of interest
 - i. Opioid misuse- A “yes” response to either of the following two items:
 1. Did you use the pain medication more than prescribed, or for a longer period than prescribed? [pnmed_longer]x
 2. Have you used prescription pain medications that were prescribed to someone else? [pnmed_othersrx]x
 - ii. Proportion of workers with lost time- A “yes” response to either of the following two items:

1. Please refer to the last 12 months for the following questions: Did you miss any days of work because of your pain or discomfort? [missday_pn]x
2. In the past 12 months, have you gone to work intoxicated, high, or recovering from the night before? [missday_intox] [*possible reduced productivity]x
- iii. Proportion of workers who are willing to seek help
 - 1) their workplace
 1. If I was struggling with a substance use problem... I would be willing to seek help from my supervisor or someone in human resources [help_sup_hr]x
 2. If I was struggling with a substance use problem... I would be willing to seek help from a professional (MAP or behavioral health) [help_prof]x
 3. If I was struggling with a substance use problem... I would be willing to ask a trusted coworker for help [help_coworker]x
 4. Have you attended Alcoholics or narcotics anonymous (AA/NA) group [aa_na_use]x
 5. Have you met with the specialist? [peer_supp_use]x

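### The survey endpoint labelled 'opioid misuse' scores misuse of any prescription pain medication, so non-opioid misuse is counted and a fall in opioid misuse is diluted by an unknown amount

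*Combined protocol and SAP*

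**What the plan says.** Section 9.4.2 b) defines the survey primary endpoint thus: "Opioid misuse- Participant responded yes to one of the following two questions". The first item, pnmed_longer, is "Did you use the pain medication more than prescribed, or for a longer period than prescribed". The second, pnmed_othersrx, is "Have you used prescription pain medications that were prescribed to someone else".

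In the worker survey (Section 10.2, item B), the medication that pnmed_longer refers to is set by an earlier question: "Have you been prescribed (by a doctor) any pain medication? CHECK ALL THAT APPLY". Its options are Vicodin, OxyContin, Tylenol 3 with codeine, Percocet, Darvocet, Morphine, Hydrocodone, Oxycodone, Other, and none prescribed. Over-the-counter medicines have their own question ("Have you taken any over-the-counter medications to manage your pain"), which is not scored.

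The data management appendix introduces the survey derivations with "We will examine the items related to each of the three outcomes of interest" and repeats the same two items. It applies no condition on which product was ticked.

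**The concern.** The label and the items describe different things. Section 2.2 describes misuse as taking opioids other than as prescribed, and the claims side of the appendix identifies opioids by pharmacy class. The survey score has no such restriction. A worker who takes a prescription anti-inflammatory longer than prescribed, or borrows a relative's, is counted as an opioid misuser.

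The error need not stay constant between waves. The guidelines being tested tell funds to "Minimize early exposure to opioids by offering non-opioid and non-pharmaceutical pain management options", and they add: "Alternative treatments may include nonsteroidal anti-inflammatory or non-pharmaceutical treatments". If some members move to a prescription non-opioid and misuse that instead, they remain positive although their opioid misuse has ended.

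What is at stake is the reported level, the reported change, and the planning of the next trial. Sections 5.5, 9.1 and 9.2 all say that these data will inform a future power calculation. A proportion carrying the wrong label would pass straight into it.

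**Working it through.** **Plan's own figures.** The survey count in Section 9.2 reproduces: 300 surveys × 3 funds × 2 time points = 1800. The plan gives no figure for the share of positive answers that involve no opioid, so there is nothing to reproduce on the point itself.

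**Where non-opioids can enter.**
- *pnmed_longer.* The eight named products are opioids or opioid combinations (general drug knowledge; the survey does not say so). Non-opioids therefore enter only through 'Other', which also holds any unlisted opioid.
- *pnmed_othersrx.* There is no drug list, so any prescription pain medication qualifies, and the answers collected cannot be separated afterwards.

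**Inputs for an illustration.**
- Section 2.2: 34% of people aged 18–64 used prescription opioids in the past year, and 17% of those reported misuse. These are national figures, not figures for union members.
- p = 0.34 × 0.17 = 0.0578, or 5.78% with opioid misuse; 0.0578 × 300 ≈ 17 respondents per fund per wave.
- R = 30%: assumed share of opioid misusers who switch away from opioids.
- f = 10%, 25% or 50%: assumed share of baseline positives that are non-opioid only.
- r = 0, 0.5 or 1: assumed share of those who switch and then misuse a prescription non-opioid.

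**Formulas.** Measured baseline M0 = p/(1 − f). Measured follow-up M1 = p(1 − R) + pRr + (M0 − p). The measured relative fall is then (M0 − M1)/M0 = R(1 − r)(1 − f).

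**With opioid-only scoring.** The score falls from 5.78% to 0.0578 × 0.70 = 4.05%, the full 30%.

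**With the current items.**

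| f | M0 | M1, r = 0 | Relative fall, r = 0 | Relative fall, r = 0.5 |
|---|---|---|---|---|
| 10% | 6.42% | 4.69% | 27.0% | 13.5% |
| 25% | 7.71% | 5.97% | 22.5% | 11.25% |
| 50% | 11.56% | 9.83% | 15.0% | 7.5% |

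At r = 0 the absolute fall is the same in every row: 0.30 × 5.78 = 1.73 percentage points. A stable background of non-opioid misuse thus raises the level and shrinks the relative change, but leaves the absolute change alone. The absolute change shrinks only when replacement drugs are misused; at r = 0.5 it is 1.73 × 0.5 = 0.87 points. The measured fall is zero only at r = 1.

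**The case against.** The case for leaving the endpoint alone has real force.

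- **The leak in the first item is narrow.** The tick list consists almost entirely of opioids and so cues them, and 'Other' may hold unlisted opioids as well as non-opioids. This stands, and it is why no size can be given. It does not help the second item, which has no list.
- **Substitution is mostly toward things that are not scored.** The guideline strategy quoted above goes on to list physical and psychological treatments. The anti-inflammatories mentioned there are not said to be prescription ones, and over-the-counter use is a separate, unscored question. This also stands: only members who misuse a prescription non-opioid remain counted.
- **The trial is a feasibility study.** It has no formal hypothesis test and no power calculation, and success means recruiting funds and collecting measures (Sections 3, 9.1, 9.2). The companion claims endpoint is built on opioid fills. This limits the harm within the trial but does not protect the future power calculation.
- **A definition may appear elsewhere.** The opening of the survey instrument was not in the text available, so an introductory definition of pain medication cannot be excluded. None appears with the items, in 9.4.2 or in the appendix.

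Two stronger readings are tempting. A reader might infer that a switch to non-opioids cannot lower the endpoint. It can: anyone who takes the new drug as prescribed, or moves to over-the-counter or non-drug care, and gives no yes on the second item leaves the numerator. A reader might also infer that non-opioid use as such is scored. It is not: the first item requires over-use, and the second requires someone else's prescription.

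**Conclusion.** The mismatch is real on the face of the plan. As written, misuse of a prescription non-opioid is reported as opioid misuse, and a fall in opioid misuse is diluted to the extent that workers misuse a prescription non-opioid instead. It is not abolished.

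The size is unknown. The 27%, 22.5% and 15% that a true 30% relative fall would show as rest on assumed non-opioid shares of 10%, 25% and 50%, and on no misuse of replacement drugs. They illustrate the direction and are not estimates. Applying the 17% rate from Section 2.2 to non-opioid users, to work out what share of positives is false, would not be supported: that rate describes opioid users, and the documents do not say how many members hold only non-opioid prescriptions.

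The conclusion assumes that no definition in the opening of the survey limits pain medication to opioids. The sponsor can check this directly.

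**What to change.** In Section 9.4.2 b) and the survey part of the data management appendix:

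1. Label the two-item score 'prescription pain medication misuse', and do not report it as opioid misuse.
2. At both waves, report pnmed_longer split by the product list already collected: at least one named opioid ticked, versus 'Other' only. Use the named-opioid figure as the opioid-specific estimate.
3. Report pnmed_othersrx separately, as use of someone else's prescription pain medication. Add '(opioid)' with product examples only if neither wave has been collected, so that both waves use the same wording. Section 8.1 describes survey collection in the past tense, so this option may be closed.
4. When planning the future trial, carry forward the named-opioid figure and the range up to the two-item score. The gap also contains borrowed medication, so it is a planning range and not an estimate of non-opioid misuse.

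The cost is relabelling and one extra tabulation from data in hand. There are three drawbacks. Unlisted opioids under 'Other' are missed in the restricted score. Workers who tick both a named opioid and 'Other' remain ambiguous. The opioid-specific prevalence will be lower. Keeping the two-item score under its accurate label means that borrowed medication, which may include opioids, is not lost from the report.
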